Six NHs will participate in audio recording of CNA communication before and after CHATO (see letters of support). These NHs will be randomly assigned to immediate feedback (n=3; recording with app feedback on elderspeak use) or control (n=3; recording with end of study feedback) groups. In each NH, 12 CNAs will be recruited using strategies successful in our past research such as announcing the research opportunity at staff meetings. Enrollment of 12 CNAs per NH allows for levels of attrition experienced in our prior studies. If fewer than 30 CNAs per group complete recordings, more NHs will be added. CNA volunteers (at least 30 per group) will record their communication in 2-hour care sessions on 1 day before and on 3 days after completing CHATO.

In both NH groups, 12 CNAs will be recorded for a 2-hour shift prior to participating in CHATO training (baseline). The URL link to complete the CHATO modules will be provided for the CNAs as well as other NH staff. Staff will be expected to complete the training over a 2-week period. After completion, the 12 CNAs from each NH who are participating in the app testing will be recorded again within a week of completing training (post-CHATO time 1), then approximately 1 week later (post-CHATO time 2), and finally another week later (post-CHATO time 3). Immediate feedback NH CNAs will receive the app feedback at the end of each post- CHATO recording session, while control group NH CNAs will not receive app feedback until the end of their post-CHATO time 3 recording sessions.

Each NH will provide a letter of interest, acknowledging random assignment, committing to engage staff in CHATO training, and agreeing to provide descriptive and cost data including number and types of staff and average wages. Each NH will be approved prior to participation by the KUMC IRB. NH size and census, profit status, proportion of residents with dementia, presence of a special care unit, staffing and turnover ratios, Medicare star rating, antipsychotic prescription rate, and Medicaid case mix will be collected from Nursing Home Compare and NH reports. Medicaid case mix is a measure of resident acuity or care needs that is used to determine Medicaid reimbursement rates and has been used in research to control differences in care needs across NHs.^{67,68} Participating NHs will be encouraged to engage all direct care staff, including housekeeping, dietary, and administrative staff in the training.

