CHATO is presented in three modules.^{10,70} Session 1 introduces effective versus ineffective communication. Participants identify communication issues in video vignettes. Session 2 focuses on identification and negative effects of elderspeak, using video-recorded examples. Session 3 includes strategies for improved communication based on assessment of each resident's abilities. Participants critique communication in videos and correct transcripts to eliminate elderspeak. Training is limited to three 1-hour sessions to assure feasibility in busy NHs. The modules include moderated discussion and interactive exercises that must be completed to advance through the program. This assures content fidelity and dose of the intervention. CHATO is provided to as many staff as possible to achieve facility-wide effects of reduced elderspeak.⁷⁴ The modules contain pre- and post-tests (scenario-based questions and rating of staff communication in video clips) to evaluate knowledge gain. The Modified Duke Diffusion of Innovation⁷⁵ survey provides information about CHATO participant intentions to use learned skills in practice and the likelihood for translation.

Audio Recordings. CNAs will be recorded for 2 hours on 1 day in the week before and 3 days in the 2 weeks after CHATO training. To ensure consistency, every attempt will be made to make post-CHATO recordings at the same time of day. CNAs will be permitted to turn the recording unit off when they do not wish to be recorded. Although this may limit validity of the recordings, it assures privacy and participation. Recordings will be time coded and take place during morning care when elderspeak and BPSD are most frequent.^{44,76,77} To minimize attrition, CNAs will be recruited just prior to their NH's participation in CHATO training. *A priori* randomized order for NH participation will control for historical effects. Intention-to-treat analyses will be used. The feedback group CNAs will receive automated feedback on elderspeak use after each post-CHATO recording session. The control group will receive feedback for all recording sessions after their final (third post-CHATO recording session). The Project Director will download recordings for both groups and delete them from the iPod Touch.

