- b. **New Developments:** The PI and SMC will monitor media, professional presentations, and scientific literature for breaking scientific developments regarding new developments, safety, and ethics that could impact the study. These will be reviewed at each annual SMC meeting. The SMC will evaluate the final study manuscripts and final reports to assure results are fairly presented and conclusions are appropriate.

III. Subject Participation

A. Recruitment:

1. Recruitment will be conducted at the 7 nursing homes involved in the study. The feasibility nursing home is in Kansas City, KS and the 6 nursing homes in the clinical trial are on the Western Slope of Colorado. All the staff at the nursing homes will be invited to participate in the CHATO training and 12 CNAs at each nursing home will be recruited to evaluate the feedback app effects.
2. The PI and Project Director will work directly with the leadership and staff at the nursing homes to recruit voluntary participants. Presentations at staff meetings will be conducted to inform direct care staff at the nursing homes of the training, app, and research. An information sheet about the project will be provided to staff. The project director will meet with interested CNAs to further explain research, answer questions, and gain consent.

B. Screening Interview/questionnaire: CNAs who participate in audio recording will be at least 18 years old (have legal right to provide consent), speak fluent English, and be permanently employed in the NH. The Project Director will meet with interested CNAs and confirm they meet the eligibility criteria.

C. Informed consent process and timing of obtaining of consent

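### The plan does not conceal a nursing home's arm while its nursing assistants are recruited, consented and recorded at baseline, so volunteers could differ by arm; the arm could be withheld at almost no cost.

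*Combined protocol and SAP*

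**What the plan says.** Section II.B, Preliminary Effects Testing, describes assignment first: "These NHs will be randomly assigned to immediate feedback (n=3; recording with app feedback on elderspeak use) or control (n=3"). The next sentence turns to enrolment: "In each NH, 12 CNAs will be recruited using strategies successful in our past research". The same part provides for further homes if a group ends with fewer than 30 completers, and gives no method for assigning them.

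Section II.B, Audio Recordings, times enrolment: "To minimize attrition, CNAs will be recruited just prior to their" home's start of CHATO. It adds that an a priori "randomized order for NH participation will control for historical effects".

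Section III.A names the recruiters: "The PI and Project Director will work directly with the leadership and staff at the nursing homes to recruit voluntary participants". On consent it says: "The project director will meet with interested CNAs to further explain research, answer questions, and gain consent". Section II.K also gives eligibility and consent to the Project Director, and names that person as present during study procedures.

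Section II.B, Psycholinguistic Coding, states blinding to group and time point for the research assistants. No one else is said to be blind.

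Baseline recording and CHATO are the same in both groups. The arms first part after CHATO: "Immediate feedback NH CNAs will receive the app feedback at the end of each" post-CHATO session, while controls get theirs after the third. Section V.C describes feedback to participants as coming either straight after recording or at study end, according to group.

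**The concern.** Randomising homes balances the homes, in expectation. It does not balance the people who volunteer within them if they volunteer after the arm is known. Here enrolment is voluntary and staggered home by home, and a field member presents the study in person. What differs between arms is whether a CNA sees an assessment of her own speech straight away, and section II.F recognises that being recorded, and having one's performance revealed, can worry staff. If the arm is known, the recruiter may present the study differently, or CNAs keen on prompt feedback may come forward more readily in one arm.

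The group contrast would then mix the effect of the app with a difference in who enrolled. Section II.C says that Aim 2 will estimate effect sizes for a larger study, so a distorted estimate would carry forward into its planning.

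**Working it through.** **1. Sequence, as far as the text gives it**

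- Arm generated: described before CNA recruitment in II.B, with no date or event attached.
- Arm disclosed: not stated, to anyone.
- CNA recruitment and consent: shortly before the home's CHATO training (II.B, III.A).
- Baseline recording: before CHATO, the same in both arms.
- CHATO: expected to take 2 weeks, the same in both arms.
- Post-CHATO time 1: within a week of completing training. The recording precedes any feedback, and the arms differ only once the session ends.

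So the arm could stay sealed through consent, baseline and training without altering any procedure.

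**2. What the existing safeguards cover**

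- Randomisation of homes: differences between homes, not who volunteers once the arm is known.
- Intention-to-treat (II.B): keeps CNAs in their group after enrolment, and cannot act before it.
- Blind coding: measurement of the outcome, not enrolment.
- Baseline diminutive use as a fixed effect (II.C): differences visible in one 2-hour session, not motivation or response to feedback.
- Randomised order of homes: calendar effects, not arm.

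**3. The plan's power figure, and why the fix leaves it alone**

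Inputs from II.C: 30 per group, m = 10 per home, coefficient of variation of cluster size 0.25, ICC 0.001 to 0.01, two-sided alpha 0.05, degrees of freedom by subjects (58).

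Design effect = 1 + ((0.25² + 1) × 10 − 1) × ICC = 1 + 9.625 × ICC.

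- ICC 0.001: design effect 1.0096; standard error √(2/30 × 1.0096) = 0.259; noncentral t power at 0.74 SD is 80.1%.
- ICC 0.01: design effect 1.096; standard error √(2/30 × 1.096) = 0.270; power at 0.76 SD is 78.9%.

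Both agree with the stated 80% to within about one point. Concealing the arm changes none of these inputs.

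**4. Illustration of size (the shifts are assumptions; no document supports any value)**

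Suppose the app has no effect, but differential volunteering leaves a residual between-arm shift. With the settings of step 3, the chance that the nominal 5% test rejects is as follows.

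| Assumed shift (SD) | ICC 0.001 | ICC 0.01 |
|---|---|---|
| 0.1 | 6.7% | 6.5% |
| 0.2 | 11.8% | 11.3% |
| 0.3 | 20.6% | 19.4% |
| 0.4 | 32.9% | 30.7% |

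Enrolling more CNAs would not remove such a shift. The table shows how sensitive the test would be, not what to expect.

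**5. Limit of concealment under a fixed 3:3 split**

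Assume that homes run one after another, earlier arms are known, and all 20 orders of three and three are equally likely. Once one arm is full, the remaining homes can be deduced. That leaves one deducible home in 12 orders, two in 6 and three in 2, a mean of (12×1 + 6×2 + 2×3)/20 = 1.5 of 6. A home added because one group is short would also have an evident arm if it were simply placed in that group. Neutral recruitment text still protects the CNAs in such homes.

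**The case against.** The strongest reply is that the plan may already do this correctly. No sentence says that the arm is disclosed before consent, or that the Project Director knows it when recruiting. The recruitment sentence is tied to CHATO training and gives limiting attrition as its reason; the a priori randomised order concerns calendar order. A reader might infer from the order of two sentences in II.B that CNAs are enrolled after assignment by an unblinded recruiter, but the documents do not establish that. This stands, and it limits the point to absence of stated concealment.

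A reader might also infer that CNAs uneasy about feedback could avoid it by being in a control home. They could not: controls receive feedback on all sessions after the third post-CHATO recording, and the app's feedback is private in either arm. The difference is one of timing, so the incentive to volunteer differently is weaker than in a feedback versus no-feedback comparison. This stands too.

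The consent pages are not in the public copy, so what CNAs are told cannot be judged, and V.C suggests that neutral wording is close to hand. The remark in II.D that volunteers self-select is about representativeness, not about a difference between arms, and is not evidence of bias.

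Finally, Aim 2 is preliminary, coding is blind, and the model already adjusts for baseline use and may add sex, knowledge gain and other CNA characteristics. These reduce some risks, but none measures willingness to change or openness to prompt feedback at enrolment.

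**Conclusion.** The point holds as a gap in procedure, not as a demonstrated bias. The plan places assignment before recruitment in its narrative, has the field team recruit and consent home by home, and states blinding only for the coders. It therefore leaves differential volunteering by arm open, and none of its safeguards closes it. The conclusion rests on reading silence about concealment as no planned concealment; if an allocation procedure exists elsewhere, stating it would settle the matter.

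The size is not estimable from the documents, and the assumed shifts in the table should carry no weight in judging it. The case for acting rests on the design: nothing differs between arms until the end of the time 1 session, so withholding the arm until baseline is complete removes a source of bias and gives up almost nothing. It should be settled before the first home recruits.

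**What to change.** - Have someone outside the field team, such as the study statistician, hold each home's arm, including that of any home added to reach 30 completers. State how added homes are assigned.
- Release a home's arm only after all its CNAs have consented and completed baseline, preferably not until its time 1 sessions begin.
- Use one recruitment and consent text in all homes, saying that feedback comes either after sessions or at the end of the study, in line with section V.C.
- State in II.B and III.A the order of consent, baseline and disclosure, and who knows the arm at each step.
- Report the time 1 contrast from the planned group-by-session model as a pre-feedback check. Note its limits: time 1 sessions may be staggered within a home, so colleagues can learn the arm from those recorded earlier, and with three homes per arm a difference cannot separate selection from chance imbalance.

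The cost is protocol and consent wording and a held list, with no change to sample size, visits, alpha or power. The Project Director learns each home's feedback setting later, and the arms of the last homes may still be deducible.

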Recording equipment: To create high fidelity recordings for optimal natural language processing, each CNA volunteer will wear a hypercardioid condenser headset microphone with unidirectional sound sensitivity. This microphone assembly is designed to pick up sound directly in front of the microphone and to reject off-axis background sounds such as from residents and staff. In addition to using microphone hardware to isolate the user's voice, the app uses digital noise gating and frequency level stabilization to limit extraneous content and to support audio quality. An iPod Touch with password encryption will be carried in the pocket of the CNA volunteer. The iPod Touch will be connected to the microphone by a standard 3.5 mm headphone jack. The battery life of the iPod Touch enables continuous use during the 2-hour recording window for each CNA.

iOS App: The iPod Touch will run an iOS app that records and processes audio in real time and utilizes voice activation frequency technology to isolate and record when a user is speaking and discard periods of silence from the recording analysis. Original back-up recordings are saved locally on the secured iPod Touch for the Project Director to access through a master password within the app to all user accounts. Together, the iPod Touch and low profile, lightweight headset microphone will provide high quality audio for maximal analytic accuracy and minimal workflow interruption or reaction by residents and staff. The initial 15 minutes of each recording session will be discarded to allow CNAs time to adjust to being recorded. Recordings will be analyzed in real time using a transcription detection model powered by Amazon Transcribe. All speech-related data are communicated using Transport Layer Security protocols to ensure end-to-end security and HIPAA compliance. Transcripts will be downloaded to the iPod Touch app that identifies and tabulates diminutives, displaying a feedback infographic at the end of the session.

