Data Archiving. After each recording session, the Project Director will screen and edit recordings to delete any resident or other staff communication or other identifiers (names) so that the archived recording contains only the desired CNA participant's voice. Recordings and data will be archived in a dedicated research computer labeled with unique identifier codes. To reduce the Hawthorne effect, the initial 15 minutes of each recording session will be discarded. An estimated hour of recorded speech will be collected four times for each of

60 CNAs, providing approximately 240 hours of recordings for transcription, coding, analysis, and additional app algorithm training.

Psycholinguistic Coding. RAs will transcribe all recordings (for both groups) and will use brackets to code diminutives using our established operational definitions and protocols.^{10,43,45,56,78} To assure reliability, as used in our past studies, RAs will be trained on a practice sample until achieving 90% agreement for utterance segmentation and coding. A second trained coder will independently code 10% of the actual study transcripts. Additional training will be provided if agreement falls below 85%. Systematic Analysis of Language Transcripts (SALT)⁷⁹ will be used to tabulate frequencies for each code. Data will be entered in an electronic spreadsheet using unique identifier codes and stored on a secure computer. RAs will not have access to the key connecting codes with identifying information and will be blind to group assignment and assessment time points.

Acceptability and Cost Testing (Aim 3): CNAs testing the app will complete the System Usability Scale (SUS), a validated 10-item industry standard survey to rate (1) use of the microphone, recorder, and app; (2) acceptability and work compatibility; (3) feedback infographic; and (4) interest in self-monitoring. We hypothesize that staff who use the app will find it acceptable and beneficial for their practice. As in our prior studies, we will use process-based costing to determine average costs for using the SPEEKO for Elderspeak feedback app, comparing costs relative to any difference determined for reductions in diminutive use in the immediate and delayed feedback groups.^{80,81} Evaluation of acceptability and costs are key factors in consideration of ongoing plans for app dissemination in NHs and across other long-term services and support settings.

C. Sample size, statistical methods, and power calculation

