Aim 1: We will demonstrate feasibility, acceptability, and validity of the SPEEKO for Elderspeak feedback app with detection model algorithm optimization with a diminutive accuracy testing benchmark of 80% or higher. App outputs will be compared to data from transcription and psycholinguistic coding, using our established protocols, to validate app reliability for diminutive detection. Also, an analysis of a CNA-completed, 10-item usability scale (The System Usability Scale) with an acceptability benchmark of 50% or higher.

Aim 2: Linear Mixed Models (LMMs) or Generalized LMMs, depending on the distribution of each outcome, will be developed to determine the impact of group assignment (feedback or no feedback) on use of elderspeak diminutives. Baseline diminutive use, group (feedback vs. no feedback), recording session (pre- and post CHAT sessions 1, 2, and 3), and interaction between intervention and session will be fitted as fixed effects. To account for clustering, each NH will be fitted as a random effect. To account for correlation due to repeated measurements, an appropriate covariance pattern will be determined from data. CNA and resident sex and CNA knowledge gain will be tested as covariates. Aim 2 will estimate variability, effect sizes, and intracluster correlation for a future larger-scale study. Sample sizes of as few as 30 in each group, or 10 CNAs on average in each NH, will achieve 80% power to detect a difference between the group means of 0.74 to 0.76 standard deviations, assuming the intracluster correlation coefficient ranging from 0.001 to 0.01 and coefficient of covariation among cluster sizes of 0.25. A two-tailed t-test was used with a significant level of 0.05 and the degrees of freedom based on the number of subjects.

Aim 3: We will use process-based costing to determine average costs for using the SPEEKO for Elderspeak feedback app, comparing costs relative to any difference determined for reductions in diminutive use in the immediate and delayed feedback groups.^{80,81}

D. Subject Criteria (See Vulnerable Populations appendix, if applicable):

1. Inclusion criteria: We will recruit CNAs who are age 18 or older, permanent employees, and fluent in English to participate. Descriptive information (age, sex, race, ethnicity, role, experience) will be used to identify CNA covariate factors predicting communication

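### Does the Aim 2 analysis need a stated denominator for diminutive use?

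*Combined protocol and SAP*

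**What the plan says.** Section II.B (Psycholinguistic Coding) has assistants transcribe every recording and code diminutives; the SALT software "will be used to tabulate frequencies for each code". Coders are trained "until achieving 90% agreement for utterance segmentation and coding".

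Section II.C (Aim 2) models the effect of group on diminutive use with a linear or generalised linear mixed model, chosen by the outcome's distribution. The fixed effects begin "Baseline diminutive use, group (feedback vs. no feedback), recording session (pre- and post CHAT sessions 1, 2, and 3" and add the group-by-session interaction. Nursing home is a random effect; sex and knowledge gain are candidate covariates. No unit, offset or exposure term is named. Section V.A (Aim 2) repeats only the model type.

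On how much is recorded, Section II.B (Audio Recordings) sets 2-hour sessions and adds: "Recordings will be time coded and take place during morning care". The first 15 minutes are dropped. It also says "CNAs will be permitted to turn the recording unit off when they do not wish to be recorded", and comments: "Although this may limit validity of the recordings, it assures privacy and participation". Under iOS App, voice activation is used to "isolate and record when a user is speaking and discard periods of silence from the recording analysis". Data Archiving expects roughly an hour of speech per session.

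**The concern.** A tabulated frequency can be compared between arms only if each session offers a similar opportunity to produce the event. Here opportunity is not fixed. A nursing assistant who switches off for half an hour contributes fewer diminutives without speaking any differently. If raw counts were modelled, two things could happen.

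- **Noise.** Variation in recorded time inflates the variance of the group contrast even when it is balanced between arms.
- **Bias.** If the feedback arm recorded less, fewer diminutives would look like an effect of feedback; if it recorded more, a real effect would be diluted. Such a difference could be caused by feedback only at the second and third post-training sessions, because "Immediate feedback NH CNAs will receive the app feedback at the end of each post- CHATO recording session".

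Aim 2 is also meant to supply variability and effect sizes for a larger study, so the scale chosen here would carry forward.

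**Working it through.** **1. The plan's own power figure.** Inputs from Section II.C: 30 per group, 10 per home, intracluster correlation (ICC) 0.001 to 0.01, cluster-size coefficient of variation (CV) 0.25, two-sided 0.05, degrees of freedom from subjects (60 − 2 = 58).

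Design effect = 1 + [(1 + 0.25²) × 10 − 1] × ICC = 1.0096 at ICC 0.001 and 1.0962 at ICC 0.01.

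The difference detectable with 80% power is 0.739 SD and 0.770 SD by the noncentral t (0.727 and 0.757 by the normal approximation). Power at the stated 0.74 SD with ICC 0.001 is 80.1%. At 0.76 SD with ICC 0.01 it is 78.9% (t) or 80.3% (normal). The statement reproduces. Being in SD units, it holds for a count, a rate or a proportion alike, so it neither reveals the scale nor depends on it.

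**2. Noise with recorded time balanced between arms.** The documents give no mean count, no spread of rates and no spread of recorded time, so every input here is assumed: mean count μ = 10, between-person rate CV 0.7, lognormal exposure with CV c. With counts Poisson given rate and exposure, the squared CVs are:

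- counts: (1 + 0.7²)(1 + c²) − 1 + 1/μ
- rates: 0.7² + (1 + c²)/μ

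| c | counts | rates | ratio |
|---|---|---|---|
| 0.10 | 0.6049 | 0.5910 | 1.02 |
| 0.15 | 0.6235 | 0.5923 | 1.05 |
| 0.25 | 0.6831 | 0.5963 | 1.15 |
| 0.50 | 0.9625 | 0.6150 | 1.57 |

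For mean counts of 5 to 20 the ratio runs from 1.12 to 1.17 at c = 0.25, and from 1.44 to 1.65 at c = 0.5.

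Simulated power used 20,000 trials per case, 30 per arm, no clustering, and analysis of covariance of the mean of the three post sessions on baseline. Within-person log-correlation was 0.7 for rates and 0.5 for exposure. With a true 40% rate reduction at sessions 2 and 3:

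| c | counts | rates |
|---|---|---|
| 0.10 | 65% | 66% |
| 0.15 | 64% | 66% |
| 0.25 | 60% | 66% |
| 0.50 | 46% | 63% |

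This test is simpler than the Section II.C model, which has session and interaction terms, so the figures are illustrative.

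**3. Bias, as a hypothetical.** Suppose the feedback arm had 20% less exposure at sessions 2 and 3 with equal rates. The ratio of mean counts over the three post sessions is (1 + 0.8 + 0.8)/3 = 0.867, a false reduction of 13%. At c = 0.25 counts reject in about 17% to 18% of trials and rates in 5%. With 10% less exposure the ratio is (1 + 0.9 + 0.9)/3 = 0.933, and counts reject in about 8%. With 25% more exposure and a true 40% rate reduction, the count ratio is (1 + 0.75 + 0.75)/3 = 0.833, against (1 + 0.6 + 0.6)/3 = 0.733 for rates; power is about 26% for counts and 66% for rates. Nothing in the documents points to any such difference between arms.

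**4. Which sources of variation count.** Discarded silence holds no diminutives, so removing it cannot lower a diminutive count. What shortens observation is switching off (or a technical failure). How much a person talks while the recorder runs is behaviour. If feedback led staff to say less and so use fewer diminutives, the drop in count would be real. The hypothetical figures in step 3 are errors only if exposure means recorded time, or if the target is taken to be use per unit of speech.

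**The case for a change.** The strongest case for a change is that the omission is plain and cheap to close. No section names the unit, and Section II.C lists its model terms in enough detail that a missing offset is noticeable. The plan itself concedes that switching off may limit validity, and it sets no minimum recording time. The earlier trial's percentage scale appears only as background in Section I.B, the cited coding protocols are not reproduced, and the option of a generalised model permits an offset without requiring one. A sentence would settle the unit before results are seen and would fix the scale of the effect size passed to the next study.

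All of that stands as a description of what is unwritten. It does not show that a stated rule or figure gives a wrong answer. Nor is the obvious remedy clearly better. Diminutives per utterance or per word is a different target from diminutives per standard care session, and feedback may change its denominator after randomisation. Recorded time is the denominator that speaks directly to switching off. No per-speech or per-minute rate cures selective switching off, when staff pause recording at the moments they would use diminutives. The denominator is a matter of judgement.

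**Conclusion.** This is missing detail that a competent analyst will fill, so no change follows. The plan neither prescribes raw counts nor excludes a rate. The choice of model waits on the outcome's distribution, the team reported elderspeak as a percentage in its earlier trial, and Section II.B relies on established protocols for data reduction and coding. Sessions share a fixed length and time of day, and time codes and segmented utterances allow recorded time or amount of speech to be derived without new data.

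The size cannot be estimated from the documents. Under the assumed inputs, modelling counts costs 1 to 2 points of power if recorded time varies modestly (CV 0.10 to 0.15), about 6 points at 0.25 and about 17 at 0.5. The larger bias figures need an imbalance between arms for which there is no evidence. The stated 0.74 to 0.76 SD is untouched, and Aim 2 is described as preliminary.

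The conclusion rests on the analysts settling the unit with recorded time in view. Recorded time turning out to differ materially between arms would reopen the question at analysis.
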